This section records all changes made to the protocol for a specific study. In the table below, record each and every relevant change by indicating what changes were made.

Revision	Date (DD/Mmm/YYYY)	Revision Author	Comments/Changes
1.0	01/Jul/2015	[name]	Clinical writer – Draft finalized based on 28-29/May GE-NFL Medical Advisory Board (MAB) and GEHC internal reviewer comments.
2.0	28/Sep/2015	[name]	Clinical writer – Revised as per APPENDIX F – AMENDMENT TO PROTOCOL VERSION 1.0 TO 2.0 .
3.0	26/May/2016	[name]	Clinical writer – Revised as per APPENDIX G – AMENDMENT TO PROTOCOL VERSION 2.0 TO 3.0 .
4.0	14/Nov/2016	[name]	Clinical writer – Revised as per APPENDIX H – AMENDMENT TO PROTOCOL VERSION 3.0 TO 4.0 .

STUDY SYNOPSIS

Study Title: Advanced MRI Applications for Mild Traumatic Brain Injury - Phase 2**Study Number:** 114-2015-GES-0017**Research Type:** Clinical (human) *parallel segments of mTBI patients and non-TBI volunteers aged ≥15 and ≤50 years old at the time of enrollment***Investigators/ Study Sites:**¹ Up to nine (9) sites may be included in this study, as listed in Appendix 1 – Study Site and Investigator List.

Study Sponsor: GE Healthcare (GEHC) Sponsor Contact: [name], Senior Clinical Affairs Project Manager	Address: [name] [contact] E-mail: [contact]
Research Manager Name: [name] Clinical Study Program Manager, GE/NFL Head Health Initiative	Address: [name] [contact] E-mail: [contact]
Medical Monitor Name: [name] Executive Medical Director	Address: [name] [contact] E-mail: [contact]
Brief Description of Study Purpose: This data-driven study is being conducted for hypothesis generation in population of mild traumatic brain injury (mTBI) patients using advanced applications for magnetic resonance imaging (MRI) developed by the Sponsor, GE Healthcare (GEHC), and corresponding clinical neuropsychological assessments. This data is intended for future use in development of specialized MR acquisition, reconstruction, and processing software intended to identify mTBI biomarkers.	
Summary of Study Procedures: Clinical Site Procedures: Two parallel subject segments will be enrolled, including (1) mTBI patients with recent injury in Segment 1 and (2) subjects without recent TBI injury of similar age and demographic characteristics (non-TBI controls in Segment 2). Baseline health information, demographics, and medical history (including prior TBI injury) will be collected for both segments. Subjects will attend up to four sequential visits relative to injury date (mTBI subjects) or first study scan date (controls): Visit 1 = ≤ 72 hr, Visit 2 = 7 ± 2 days, Visit 3 = 14 ± 2 days, and Visit 4 = 90 ± 7 days. The mTBI subjects (Segment 1) may start at Visit 1 or Visit 2. Each visit will include a clinical neuropsychological assessment battery and MR scan with GE Research Pack II (including research sequences and clinically useful T1, T2, Flair, and reconstructed SWI and DTI) will be evaluated by the site. Laboratory Procedures: Clinically acquired MR data (DICOM, P-files, and auxiliary files) will be transferred to an imaging laboratory for GE Research Pack II reconstruction of clinically useful views using multiband technology and study post-processing. Post-processed data and evaluations (as indicated on a per-module basis by the Sponsor) will be collected.	

FOOTNOTES CORRESPONDING TO NUMERALS IN THE TEXT

¹ The University of Michigan Site (originally Site 007) is removed due to non-participation.

Number of Subjects: Data will be collected for two groups (segments) of subjects: (1) mTBI subjects in Segment 1; and (2) non-mTBI controls in Segment 2. The target of the study is to collect at least 210 complete datasets from mTBI patients and at least 105 complete datasets from control subjects. Accounting for all possible reasons, attrition is estimated at 40%. Thus, a maximum of 350 mTBI subjects and 175 non-TBI controls may be enrolled across all sites. While it is expected that sites should enroll approximately equal numbers of subjects, if possible, all sites are encouraged to accrue eligible mTBI subjects as rapidly as possible on an ongoing basis until the maximum number of subjects across all sites is reached. Thus, it is prospectively expected that per-site accrual may vary based on actual enrollment rates.

Additionally, up to 10 volunteers without mTBI injury and not requiring urgent medical care (Segment 0 volunteer subjects) may be enrolled per-site for training and retraining purposes on study devices.

Each site should enroll approximately half as many control subjects as mTBI subjects that complete two consecutive visits and thus provide two consecutive data points (complete either Visits 1 and 2, or Visit 2 and 3), e.g., one control may be enrolled for every two mTBI subjects. A report of mTBI subject enrollment will be generated by the Sponsor or its delegated contract research organization (CRO) and provided to the site on a monthly basis (30±7 days). The report will categorically detail the number of mTBI subjects completing at least 2 visits based on (in order of priority) gender, age, handedness, highest educational level, and MR system used (if more than one system used at the site) as detailed in [Section 5.1.1. Enrollment of non-mTBI controls](#).

Controls are required to attend Visits 1 and 4, but may also attend Visit 2 and 3 when available. Per site, controls should be enrolled in a manner that achieves the same overall ratio within each characteristic category as the mTBI population that has completed two visits to date (per site, all mTBI patients enrolled from study start to date of monthly summary analysis), with the priority detailed in Table 2 of this protocol.

Device/Product GEHC Modality: Magnetic Resonance (MR)

Device/Product Description:

The device under study is the *GE Research Pack II* advanced MRI application suite developed by the Sponsor, GE Healthcare (GEHC), which consists of acquisition software executable on commercially available Discovery MR750 3.0T/Discovery MR750w 3.0T MR scanners and software for multiband image reconstruction and post-processing features (volumetry, Kurtosis, RS fMRI, RSI, and, as applicable, further advanced modules) executable on commercially available image processing workstations. *GE Research Pack II* is optimized for use with the investigational 32-channel head coil for 3.0T GE scanners (Nova Medical).

Site-owned Discovery MR750 3.0T and/or MR750w 3.0T scanners with research coils will be used for acquisition, and commercially available VolumeShare 5 Advantage Workstations (AW) will be used for reconstruction and post-processing. Conventional accessory/ancillary devices, such as alternative MR coils, padding, communication, and safety devices may be provided by the site for use in this study (or by the sponsor, if unavailable for use at any investigational site).

Regulatory Status:

Pre-Market

GE Research Pack II and the 32-channel head coil for 3.0T MR systems (Nova Medical) are investigational medical devices. When used in conjunction with GE Research Pack II, the Discovery MR750 3.0T/MR750w 3.0T MR scanners, conventional coils, VolumeShare 5 Advantage Workstation (AW), and other accessory/ancillary devices used in the study are considered investigational devices.

Post-Market

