5. STUDY SUBJECTS

5.1. Number of Subjects

Data will be collected for two groups (segments) of subjects: (1) mTBI subjects in Segment 1 and (2) non-mTBI controls in Segment 2. The target of the study is to collect at least 210 complete datasets from mTBI patients and at least 105 complete datasets from control subjects. Accounting for all possible reasons, attrition is estimated at 40%. Thus, a maximum of 350 mTBI subjects and 175 non-TBI controls may be enrolled.

While it is expected that sites should enroll approximately equal numbers of subjects, if possible, all sites are encouraged to accrue eligible mTBI subjects as rapidly as possible on an ongoing basis until the maximum number of subjects across all sites is reached. Thus, it is prospectively expected that some sites may have differing final accrual.

Table 1 – Enrollment for mTBI subjects and controls

Segment	Description	Total enrollment (all sites, N)
Segment 1	mTBI Patients are adolescents and adults who recently sustained head injury	350 total
Segment 2	non-mTBI Subjects are enrolled as a control population	175 total

Additionally, up to 10 volunteers without mTBI injury and not requiring urgent medical care (Segment 0 volunteer subjects) may be enrolled per-site for training and retraining purposes on the investigational devices.

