5.1.1. Enrollment of non-mTBI controls

Enrollment Rate: Each site should enroll approximately half as many control subjects as mTBI subjects, at a rate of approximately one control enrollment for each two mTBI subjects that complete at least two visits (1:2). Though it is prospectively expected that actual enrollment rates may vary, it is the investigator's responsibility to maintain this approximate rate in order to minimize possible bias due to variance in scanner performance ("scanner drift") and other possible confounders.

Population Matching: The study aims to achieve overall matched mTBI and control populations across sites. The overall population will be matched for characteristics identified in order of priority in Table 2. To enable sites to select control subjects that match the overall population, a report of mTBI subject enrollment will be generated by the Sponsor or its delegated contract research organization (CRO) and provided to the site on a rolling monthly basis. The report will categorically detail the number of enrolled mTBI subjects with the following characteristics (Table 2). The clinical site, under the supervision of the Principal Investigator, will be ultimately responsible for ensuring that matched controls are selected according to these criteria.

Case-Control Matching: When possible, investigators are also encouraged to enroll individually matched mTBI and control cases of potential medical interest. Priority should be given, however, to ensuring an appropriate overall population match.

Overall Population Reports:

Table 2 – Population characteristics for enrollment of non-TBI controls (Segment 2) based monthly mTBI accrual by order of priority for matching

Priority	Characteristic	Description/Unit
1	Gender	Male, or Female
2	Age (years)	≥15 to ≤18, >30 to ≤34, >18 to ≤22, >34 to ≤38, >22 to ≤26, >38 to ≤42, >26 to ≤30, >42 to ≤46, or >46 to ≤50
3	Handedness ²⁵	Left-handed (habitual or more skillful use of the left hand for writing and for most manual functions), Right-handed (habitual or more skillful use of the right hand for writing and for most manual functions), or Ambidextrous (Having equal facility in the use of both hands)

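### The control enrolment rule (about one control per two mTBI subjects completing two visits) is not tied to the 175/105 control target, and the synopsis and Section 5.1.1 differ on which mTBI subjects count

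*Combined protocol and SAP*

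**What the plan says.** **Target.** The synopsis and Section 5.1 aim for "at least 210 complete datasets from mTBI patients and at least 105 complete datasets from control subjects". One loss figure is given, without distinguishing segments: "Accounting for all possible reasons, attrition is estimated at 40" per cent. From this, "a maximum of 350 mTBI subjects and 175 non-TBI controls may be enrolled". Table 1 repeats 350 and 175.

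**Site rule, synopsis.** "Each site should enroll approximately half as many control subjects as mTBI subjects that complete two consecutive visits". A parenthesis limits the qualifying pairs to Visits 1 and 2 or Visits 2 and 3. The sentence ends with an illustration that carries no completion condition: "e.g., one control may be enrolled for every two mTBI subjects".

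**Site rule, Section 5.1.1.** The opening asks for "approximately half as many control subjects as mTBI subjects, at a rate of approximately one control enrollment". The rate is then completed as "one control enrollment for each two mTBI subjects that complete at least two visits (1:2"), with no requirement that the visits be consecutive. The investigator has the "responsibility to maintain this approximate rate in order to minimize possible bias" from scanner drift and other confounders.

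**Monthly report and matching reference.** In the synopsis the report counts mTBI subjects with two or more visits. Section 4.3 defines the matching reference in the same way. In Section 5.1.1 the report counts enrolled mTBI subjects.

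**The concern.** The control sample was sized on one base and sites are told to recruit on another. The 175 is half of the mTBI subjects enrolled; the rate that sites must keep is half of a subset of them. If any enrolled mTBI subjects fail to qualify, losses count twice for controls: once by shrinking the base that triggers control enrolment, and again through the controls' own attrition.

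The target of at least 105 complete control datasets is one of only two numerical dataset targets in the plan. The differing definitions also mean that two sites could each follow the protocol and count different numbers of qualifying mTBI subjects.

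**Working it through.** **Inputs from the documents:** 210 and 105 complete datasets, 40% attrition, maxima of 350 and 175 (synopsis; Section 5.1); one control per two qualifying mTBI subjects (synopsis; Section 5.1.1); up to nine sites (Section 4.2).

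**Input not in the documents:** L, the share of enrolled mTBI subjects who do not complete the qualifying visits. Section 6.3.2 withdraws subjects who cannot finish the first visit in its window, which raises L. Sections 6.3.2 and 6.5 let subjects who miss later visits continue, which lowers it.

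**Step 1: reproduce the plan.**
- mTBI: 210 / (1 − 0.40) = 350.
- Controls: 105 / (1 − 0.40) = 175.
- 350 / 2 = 175.

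All three agree exactly. Because 175 × 0.6 = 105 with nothing to spare, at the planned attrition the maximum is also the number needed.

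**Step 2: apply the site rule to 350 enrolled mTBI subjects.**
- Controls enrolled = 0.5 × 350 × (1 − L) = 175 × (1 − L).
- Complete controls = 0.6 × 175 × (1 − L) = 105 × (1 − L).
- Highest control attrition that still gives 105 = 1 − 105 / (controls enrolled).
- Enrolment gap per site, assuming nine equal sites = 175 × L / 9, against 175 / 9 = 19.4 planned.

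| L (assumed) | Controls enrolled | Complete at 40% attrition | Highest control attrition giving 105 | Gap per site |
|---|---|---|---|---|
| 0% | 175 | 105 | 40.0% | 0 |
| 3% | 169.75 | 101.85 | 38.1% | 0.58 |
| 5% | 166.25 | 99.75 | 36.8% | 0.97 |
| 10% | 157.5 | 94.5 | 33.3% | 1.94 |
| 20% | 140 | 84 | 25.0% | 3.89 |
| 40% | 105 | 63 | 0% | 7.78 |

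The last row is an extreme bound: it treats every mTBI subject lost under the 40% figure as lost before qualifying.

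**Step 3: compare the two definitions of two visits (no assumption about L).** mTBI subjects enter at Visit 1 or Visit 2 (Section 6.3.1), must complete that first visit, and may miss later ones.
- Entry at Visit 1: Visits 2, 3 and 4 each attended or not, 2³ = 8 patterns.
- Entry at Visit 2: Visits 3 and 4 each attended or not, 2² = 4 patterns. Total 12.
- Any two visits (Section 5.1.1): 7 + 3 = 10 qualify.
- Visits 1+2 or 2+3 (synopsis): 4 + 2 = 6 qualify.
- Patterns that change status: 1+3, 1+4, 1+3+4 and 2+4.

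A subject with three of the four visits (1, 3 and 4) counts under Section 5.1.1 but not under the synopsis. These are counts of patterns, not of subjects; the documents give no frequencies.

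**Step 4: compare the report descriptions.** The synopsis and Section 4.3 agree on two or more visits; Section 5.1.1 alone says enrolled. Within the synopsis, the report's count (two or more visits) is also not the count named in the enrolment rule (two consecutive visits).

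**The case against.** The strongest reply is that a ceiling and a pacing rate can both hold. The 175 is a maximum, the rate is approximate, Section 5.1.1 expects actual rates to vary, and its purpose is to limit drift rather than to size the group. The synopsis illustration and the opening clause of Section 5.1.1 can even be read as half of all mTBI subjects, which gives 350/2 = 175 and no conflict. Much of this stands: gaps of one or two controls per site at L of 5% to 10% could pass as approximate. It does not remove the point, because the literal completer rule never reaches 105 at 40% control attrition unless L is zero, and two readings within the same sentences are themselves the problem.

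Three stronger readings are tempting but not supported:

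- *That the control target will be missed.* L is not given, and complete dataset is not defined. Controls are expected mainly at Visits 1 and 4, so their attrition may differ from 40%. At L = 10%, control attrition of 33.3% or less still gives 105.
- *That the synopsis matching sentence itself names two bases*, because it mentions completers and then, in parentheses, patients enrolled from study start. The parenthesis reads more naturally as the cumulative time window for the completers just named.
- *That power or the study's success is at risk.* Section 8.2.4 sets no statistical pass/fail criterion, and no power or precision is stated.

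**Conclusion.** An internal inconsistency, minor to should-fix. The figures 350 and 175 are correct. The site rule delivers 175 enrolled and 105 complete controls only if every enrolled mTBI subject completes the qualifying visits. A shortfall is possible, not certain: about 158 enrolled and 95 complete at L = 10%, and 140 and 84 at L = 20%. These numbers assume that mTBI enrolment reaches 350, that the 40% applies to controls, and the stated values of L.

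Two wording conflicts need no assumption: consecutive visits (1+2 or 2+3) against any two, and enrolled subjects in the Section 5.1.1 report sentence against subjects with two or more visits in the synopsis and Section 4.3. The effect is on the number of controls and on consistent counting across sites.

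**What to change.** In the synopsis and Section 5.1.1:

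1. **Control count.** Set it at about half of the enrolled mTBI subjects, up to the 175 already planned. Alternatively, keep the completer rate as pacing only and state that control enrolment continues toward 175 until 105 complete control datasets are reached.
2. **Matching and report reference.** Use mTBI subjects with two or more visits, as in Section 4.3, in both places. Delete the consecutive-visit condition and its list of visit pairs from the synopsis, and replace enrolled in the Section 5.1.1 report sentence.
3. **If the completer base is kept without continuation,** restate both 105 and 175 at what it delivers, with the assumed two-visit completion rate shown. Otherwise the target stays contradicted.

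The cost is a short text change and no subjects beyond 175. The downside of basing the count on enrolled subjects is that the control-to-completer ratio, 175 : 350 × (1 − L), rises somewhat above 1:2: about 1:1.9, 1:1.8 and 1:1.6 at L = 5%, 10% and 20%. The pacing alternative may place the extra controls late in accrual, which fits less well with the scanner-drift rationale.

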1. PRELIMINARY INVESTIGATIONS AND JUSTIFICATION

1.1. Literature Review

Over 1.1 million traumatic brain injuries (TBI) occur in United States emergency departments annually, including 50,000 fatalities and 43.4% chronic disability.¹ Up to 31.6% of the global population will experience TBI during their lifetime.^{1, 2} In particular, mild TBI (mTBI) occurs in about 100-300 of 100,000 hospital-treated TBI cases, though actual occurrence in the general population is expected to be above 600/100,000, though many may fail to seek treatment despite potential long-term effects.³ Cases of mTBI are particularly common in the military, sports, and among motorcyclists and bicyclists, posing a major public health concern worldwide.⁴ Thus improved diagnostic and prognostic methods are necessary.

Historically, mTBI has been treated as an “event” perceived to have little or no lasting effect on central nervous and organ systems.⁵ Growing awareness of potential long-term impact of mTBI has based on recent reports of unexpectedly prolonged injury and subsequent identification of cerebral biomarkers and anatomical abnormalities has fostered awareness of mTBI, particularly in professional sports and the military.^{6, 7} Currently, TBI injuries are commonly categorized by severity as mild, moderate, or severe based on the length of loss of consciousness (LOC), alteration of consciousness (AOC), or post-traumatic amnesia (PTA).⁷ However, optimal and practicable routes for describing the interrelated factors in mTBI that play a role in clinical diagnosis, management, and outcomes of mTBI among the general population remain unclear.

While biomarkers of more severe forms of TBI are often readily apparent, mTBI is extremely heterogeneous and complex and often difficult to detect.⁸ Many clinicians and researchers now recognize that minute abnormalities following mTBI can result in potentially serious and adverse chronic conditions, including sleeping abnormalities, cognitive impairments, post-traumatic stress syndrome, increased suicide risk, depression, anxiety, and other neuropsychological effects.² Furthermore, patients recovering from mTBI have different cognitive symptoms and white matter injury at different time points relative to injury, potentially indicating compensatory mechanisms or plasticity in response to injury.^{9, 10}

Comprehensive characterization of mTBI pathophysiology using modern technologies, such as contemporary advanced magnetic resonance imaging (MRI) systems can provide precise information on brain injury magnitude and location. Unlike computed tomography systems, which are less costly but have limited usefulness in mTBI due to relatively low sensitivity to diffuse brain damage, MRI can detect characteristics of regional brain abnormalities necessary for diagnostic and prognostic decision-making.^{8, 11, 12} Using advanced MRI pulse sequence and parameter settings, optimized gradient pulses have the potential to yield critical information about cerebral injury, ranging from volumetric and structural data to specific information on neural tract function and metabolite concentrations. Significant scientific advancements, however, will be required before MRI can provide extensive and reliable data required to diagnose and predict progression of mTBI. This exploratory study is conducted to aid in identifying correlations between mTBI imaging and symptoms that can help to improve advanced MRI applications for brain injury developed by the Sponsor, GE Healthcare.

1.2. Background on Clinical Evaluations for mTBI

The challenge of drawing relationships between cerebral abnormalities observed using MRI and clinical symptoms remains one of the most pressing issues in modern mTBI research. This issue is complicated by the lack of standardization in clinical neuropsychological assessments tools for mTBI and the heterogeneity of injury. Notably, numerous different tools have been developed for assessing concussion immediately following military injury (“blast concussion assessments”) and immediately following injury in sports (“sideline concussion assessments”). Different organizations, however, have reached very different conclusions on which tool is optimal, and no universal consensus on the optimal tool has been reached. A comprehensive review by McLeod and Leach¹³ (2012) compared self-report concussion scales/checklists from 290 original articles published between 1995 and 2008 identified over 20 tools commonly cited in mTBI literature, and a number of additional commercial tools that are now available. Notably, McLeod and Leach¹³ also report that very few of these tools were created in a systematic manner that follows scale development processes and published psychometric properties.

Efforts to standardize tools for clinical diagnosis and management of mTBI include the Military Acute Concussion Evaluation (MACE) and US Department of Defense Instruction (DoDI) 6490.11¹⁴ and numerous commercially available questionnaires and tests. In research, one of the most widely used standardized tools for mTBI assessment is the National Institutes of Health (NIH) National Institutes of Neurological Disorders and Stroke (NINDS) Common Data Elements (CDE), a set of multiple domain assessments for collection of clinical and imaging information from diverse TBI patients.¹⁵ The first set of CDEs was developed in 2010 and was well-suited for hospital-based studies of acute TBI in adults. To broaden the utility of the TBI CDEs, experts were asked to update the recommendations to make them relevant to all ages, injury severity, and phases of recovery. The second version of the TBI CDEs (v.2) were developed in 2012 and were organized based on four major study types of epidemiological research: acute injury, hospitalized patients, studies of the rehabilitation for moderate/severe TBI, and mild TBI/concussion research. Many of the CDEs will overlap across study types, which allows for comparisons and meta-analysis across studies. This consistency also allows for continuity across disease areas, enabling increased efficiency and effectiveness of clinical research studies and clinical treatment, increasing data quality, facilitating data sharing, and helping educate new clinical investigators.¹⁵

